### **9) Procedures Involved**

#### **Consent/Screening/Baseline/Randomization Visit**

Consent procedures: All potentially eligible patients will meet with the study research assistant (RA) who will explain the study in clear, easy-to-understand language. The required information for informed consent will be summarized orally to the patient by the bilingual RA during the initial in-person contact and will be presented again in a comprehensive written consent/authorization form. The consent process will be conducted in a dedicated space at the primary care clinic. The study staff will adhere to the SOP: Informed Consent Process for Research (HRP-090). Specifically, during the consent meeting, the RA will explain the following study procedures: that patients will have a 50-50 chance of being in the tailored adherence intervention (TAI) or patient education (PE) session; that they will be asked to give permission for their charts to be reviewed; that participation is completely voluntary, and that not every patient is accepted into the study (this will be decided during the screening).

PROTOCOL TITLE: Tailored Approaches to Improve Medication Adherence

To ensure comprehension, subjects will be asked to repeat back to the RA the salient points of the consent form to make sure that they understand the study they are agreeing to participate in. If a participant asks for help while reading the consent, or evidences a problem in reading the consent, the RA will read and explain the consent him/her.

If the participants speak Spanish they will receive a Spanish Consent form. The Spanish consent form will be explained by the bilingual RA. A Spanish version of the consent form will be provided to the IRB once the English version is approved.

Blood Pressure Measurements: Following the consent procedures, the RA will take 3 BP measurements at 1 minute intervals using a validated automated device (WatchBp), with the patient seated comfortably for 5 minutes prior to the measurements, following AHA guidelines. The average of these 3 readings will be used as the BP measure for the baseline visit.

**Tailored Adherence Intervention (TAI) group:** Following the completion of the study measures, patients randomized to the TAI group will complete the technology-delivered tailoring survey and engage with intervention strategies that are matched to individualized adherence profile identified in the survey. After completing the program, the patients will be thanked, given reimbursement to defray transportation costs (\$20), and scheduled for the 3 month study visit.

**Three-Month (post randomization) Study Visit will be the same for both groups:** Patients will have 3 BP measurements taken using the automated BP device, have their HbA1c measured with the point-of-care device, and complete the self-report measures with the assistance of the RA in a private room in the clinic. . In order to facilitate completion of the 3-month follow-up visit, patients will receive a reminder post card containing the study contact information.

**Exit Interviews:** To evaluate the effectiveness and relevance of the intervention to the patients, we will conduct individual exit interviews with 10 randomly selected intervention participants. The interview questions will ask participants' opinion on the intervention approach. The interviews will help us determine which intervention components are most effective in assisting participants in taking their medication as prescribed, and which components of the intervention can be improved to make it more relevant to the target population. Patients will receive \$10 for completing the interviews.

## 10) Data Management

**Sample size calculation:** For the primary aim, we will recruit 10 patients of the target patient population to culturally tailor the technology-based adherence intervention to ensure saturation of themes will be reached. For the secondary and tertiary aims, we will enroll 20 patients per group (40 total); allowing for a 15% rate of attrition that will yield a final sample of approximately 15 patients per group who complete the study. Given the paucity of studies on medication adherence among Latinos and Blacks with hypertension, there is not sufficient data for power estimation. However, this pilot study will give us the opportunity to calculate the power needed to carry out a larger trial.

**Randomization and blinding:** To ensure a roughly equal assignment of patients to the two groups, we will use a block size of 4 with a permutation of 2 patients randomly assigned to each group, with the investigators blind to the permutation. Following CONSORT guidelines, (Bellg et al., 2004; Resnick et al., 2005) the randomization sequence will be generated by the statistician and kept in sealed opaque envelopes in a locked cabinet away from the study site. Once the RA has identified a patient that has met eligibility criteria and provided consent, the research assistant (RA) will call the study statistician for the patient's group assignment. All randomized subjects will be included in the analyses using intent-to-treat strategies. As is true for most behavioral interventions, the patient cannot be blinded to the group assignment. (Bellg et al., 2004) However, the RA conducting the data collection will be blinded to the patients' group assignments and a separate RA will be used for data collection

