## 2) Objectives

**Primary Objective:** To culturally tailor a technology-based individualized adherence intervention for Black and Latino patients with uncontrolled HTN or T2DM, who are non-adherent to their medications, and determine its acceptability.

**Secondary Objective:** To assess the feasibility of the methods and procedures to implement the individualized adherence intervention within a primary care practice in New York City.

**Tertiary Objectives:** To compare the efficacy of a tailored adherence intervention to a single patient education (PE) session on:

- a. Change in medication adherence at 3 months.
- b. Blood pressure (BP) reduction at 3 months.
- c. HbA1c reduction at 3 months.

**Hypotheses:** Among 40 Latino and Black patients with uncontrolled hypertension (HTN) or type 2 diabetes those randomized to the intervention, compared to those randomized to PE, will:

- a. Exhibit higher rate of adherence to their antihypertensive or anti-diabetic medications at 3 months.
- b. Exhibit a greater reduction in systolic and diastolic BP at 3 months.
- c. Exhibit a greater reduction in HbA1c at 3 months.

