### **Eligibility Criteria:**

Potentially eligible patients must (a) have uncontrolled HTN defined as BP $\geq$ 140/90 mmHg on at least two consecutive visits in the past year (or BP $\geq$ 130/80 for patients with diabetes and/or kidney disease) or uncontrolled T2DM defined as A1c $>$ 7%(Fox et al., 2015) on at least two consecutive visits in the past year; (b) have been prescribed at least one antihypertensive or oral anti-diabetic medication; and (c) self-identify as Latino or African American/Black and be  $\geq$  18 years of age.

Patients will be excluded if they (a) refuse or are unable to provide informed consent; (b) currently participate in another HTN or type 2 diabetes study; (c) have significant psychiatric comorbidity (determined by EMR and confirmed by the patient's PCP); or (d) plan to discontinue care at the clinic within the next 3 months.

Vulnerable populations including adults unable to provide informed consent, pregnant women, and prisoners will be excluded from this study.

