### **Analysis for the Tertiary Aims:**

**The effect of treatment on adherence status at 3-months.** Adherence will be measured as a continuous variable. A linear regression will be performed using the final assessment of adherence as a response and randomization group as a predictor. Other variables that may potentially have an effect on adherence such as age, gender, level of education and comorbidity will also be included if these variables are not balanced between groups by the randomization or if they are determined by univariate analysis to be significantly predictive of adherence.

**The effect of treatment on BP reduction at 3-months.** BP will be treated as continuous systolic BP (SBP) and diastolic BP (DBP) variables measured at baseline and 3-months. The effect of treatment on these variables over time will be assessed using differences in differences estimation whereby pre-intervention SBP and DBP values are subtracted from post-intervention values, and change amounts by study group are compared using t tests. The significance level will be set at  $\alpha=.05$ . Analysis of covariance will be used in place of a t test, if covariates are needed.

**The effect of treatment on HbA1c reduction at 3-months.** HbA1c will be treated as a continuous variable at baseline and 3 months. The effect of treatment on HbA1c over time will be assessed using differences in differences estimation whereby pre-intervention HbA1c values are subtracted from post-intervention values, and change amounts by study group are compared using t tests. The significance level will be set at  $\alpha=.05$ . Analysis of covariance will be used in place of a t test, if covariates are needed.

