**Data Management:** [name] will oversee the data management for this study. All data will be double entered by RAs and compared using automated comparison programs. Inconsistent data entry will be resolved against the raw data, and comparisons will continue until all inconsistency is removed. Periodically, [name] will review all data for duplicate records, illogical collection dates and contingencies, and outlier values using program syntax created for each file. Reasons for dropout and loss to follow-up will be tabulated by condition. The results of analyses using imputed values will be compared with the results obtained with only complete cases. If the results indicate that attrition is significantly related to one or more baseline variable, predicted values from a logit model will be used as a covariate in all subsequent analyses, thereby correcting for differential attrition. All randomized participants will be included using intent-to-treat analytic strategies. While randomization is expected to produce well-balanced groups, analyses will determine baseline differences between the groups on demographic or prognostic variables. If significant differences are found, these variables will be included in a logit model to predict group assignment, and predicted values from the final logit model will be used as a covariate in all subsequent analyses.

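### In a mixed HTN-or-T2DM sample, one unstratified block list leaves the arms' disease mix to chance, and the planned adjustment may not reliably remove an imbalance

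*Protocol*

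**What the plan says.** **Allocation.** Protocol Section 10 (Randomization and blinding) states "we will use a block size of 4 with a permutation of 2 patients randomly assigned to each group" and that "the randomization sequence will be generated by the statistician and kept in sealed opaque envelopes". Neither document names a stratification factor. That there is a single unstratified list is an inference from the singular wording and from the absence of any stratum.

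**Population.** The hypotheses in Section 2 concern "Among 40 Latino and Black patients with uncontrolled hypertension (HTN) or type 2 diabetes". The eligibility criteria in Section 4 admit uncontrolled HTN "or uncontrolled T2DM defined as A1c" above 7%. Two places differ. Section 9 (HbA1c measurements) joins the BP and A1c thresholds by *and* as the condition for continuing. Section 21 describes all forty patients as having hypertension.

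**Analysis.** In the tertiary-aims analysis, "HbA1c will be treated as a continuous variable at baseline and 3 months"; its change, like that of BP, is compared between arms by t test. Nothing restricts the comparison to patients with the relevant condition. ANCOVA replaces the t test when covariates are judged necessary, without a criterion. For adherence, comorbidity and similar variables enter the regression if they are unbalanced or significantly predictive. The Data Management paragraph of Section 10 adds a general rule: "If significant differences are found, these variables will be included in a logit model to predict group assignment", and the resulting score becomes a covariate in later analyses.

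**SAP.** The exploratory-outcomes paragraph has t tests on change for all three outcomes. It adds regressions that always control for baseline outcome, age, gender, SES, insurance and number of medications. Qualifying condition is not listed.

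**The concern.** If some patients enter for hypertension and others for diabetes, the qualifying condition largely governs how far BP or HbA1c can move in three months. Blocks of 4 balance the arm totals but not this factor. An arm that happens to hold more diabetic patients has more room for HbA1c to fall, whatever the intervention does, and the planned t test on change carries that difference straight into the contrast. Whether the plan then adjusts depends largely on a baseline significance test that has little power at 20 per arm, or on an undefined judgement that covariates are needed. At stake is how hypotheses (b) and (c) can be read in a pilot that Section 10 says will inform the power of a larger trial.

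**Working it through.** **Inputs from the documents.** 40 patients, 20 per arm, blocks of 4 (Protocol Section 10). Ten complete blocks of 4 give exactly 20 and 20.

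The plan's one derived figure concerns completers: "allowing for a 15% rate of attrition that will yield a final sample of approximately 15 patients per group who complete the study". But 20 × (1 − 0.15) = 17, and 15 of 20 means 25% attrition. This is a separate matter; both sizes are used below where relevant.

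**Assumptions, not in the documents.** The T2DM share; the level of the baseline test (taken as 0.05, two-sided, uncorrected chi-square); the outcome gap between disease types.

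**1. How often the mix is uneven.** If T of the 40 have T2DM and disease status is unrelated to entry order, the number in one arm is Hypergeometric(40, T, 20).

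| T | differ by ≥ 4 | differ by ≥ 6 |
|---|---|---|
| 10 or 30 | 27% | 6.5% |
| 14 or 26 | 32% | 10% |
| 19 or 21 | 20.5% | 5.6% |
| 20 | 34% | 11% |

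An even T permits only even differences and an odd T only odd ones, so neighbouring values jump. From T = 14 to 26 the chance of a difference of at least 4 lies between 19% and 34%. More lopsided odd totals go lower (T = 11: 15.5%). If T itself varies, with each arm's count Binomial(20, p), a gap of at least 20 percentage points has probability 16%, 23%, 27% and 23% for p = 0.2, 0.3, 0.5 and 0.7. With 15 completers per arm, where 20 points is 3 patients, the range is 25% to 36%.

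**2. What a significance trigger catches.** For a v b out of 20 each with a + b = 20, chi-square = 40(a² − b²)²/20⁴.

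- 12 v 8: 40 × 80²/160,000 = 1.6, p = 0.21
- 13 v 7: 40 × 120²/160,000 = 3.6, p = 0.058
- 14 v 6: 40 × 160²/160,000 = 6.4, p = 0.011

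So a 30-point gap does not trigger adjustment and a 40-point gap does. Under the binomial calculation, 69% to 84% of gaps of at least 20 points are not significant.

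**3. Effect on an unadjusted contrast.** Shift = (difference in share) × (outcome gap between disease types). The standard error at 20 per arm is √(2/20) = 0.32 SD.

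| Assumed gap | Shift at 20 points | Type I error given that imbalance |
|---|---|---|
| 0.25 SD | 0.05 SD | 5.3% |
| 0.5 SD | 0.10 SD | 6.2% |
| 1.0 SD | 0.20 SD | 9.7% |

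Averaged over all allocations the shift is zero.

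**4. What baseline adjustment recovers.** Simulation of 20,000 trials, assuming a 50% share, a baseline gap of 1.5 SD and a baseline-to-follow-up correlation of 0.5. Figures are for trials in which the intervention arm has at least 20 points more of the disease.

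| Disease acts | Change score | ANCOVA on baseline | Plus disease type |
|---|---|---|---|
| through baseline only | −0.20 SD | 0.00 | 0.00 |
| also directly (−0.5 SD) | −0.32 SD | −0.10 SD | −0.01 SD |

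**5. What stratification would do.** With two strata, a 50% share and blocks of 4, the SD of the arm difference in disease share falls from 15.8 to 3.3 points, and the largest difference seen in simulation is 10 points.

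**The case against.** Several points on the other side stand.

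- A reader might infer that the significance trigger is the only protection and that the plan would leave an imbalance uncorrected. The documents do not support that. Comorbidity can enter the adherence model on imbalance alone, ANCOVA is open for BP and HbA1c, and the SAP regressions always include the baseline outcome, which carries much of the disease-type difference. The protection is partial and unclear rather than absent: disease type is in no fixed list, the unadjusted t tests remain, and the SAP describes its regressions as comparing baseline with 3-month scores, with no arm term mentioned.
- A reader might call the comparison biased. Chance imbalance under valid randomization is not bias, and unconditional type I error is unaffected. At moderate outcome gaps the shift is well below one standard error.
- The premise may fail. Under a literal *and* in Section 9 every randomized patient has both conditions and there is no mix. Under Section 21 all patients have hypertension, though diabetes status could still vary.
- Unstratified blocking is a legitimate choice in a 40-patient pilot whose BP and HbA1c outcomes are tertiary or exploratory. Stratifying into three lists (HTN only, T2DM only, both) would give up exact 20/20 totals; with up to 2 extra per list, arm totals could reach 22 v 18. The SAP is dated 2018 and written in the past tense, so allocation is probably complete.

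None of this supports letting a baseline test at 20 per arm decide whether a plainly prognostic factor enters the model.

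**Conclusion.** The concern holds in a limited form. If the sample is mixed, a difference of at least 4 T2DM patients between arms is an ordinary event: about 1 in 5 to 1 in 3 allocations for 14 to 26 T2DM patients among the 40, and about 1 in 6 on average at a 20% share. The significance trigger would pass over most such differences, and the remaining provisions are too loosely worded to be relied on to remove them. The consequence is loss of precision and harder interpretation of exploratory outcomes. It is not invalid inference, and the absence of stratification is not in itself an error. The size depends on two quantities the documents do not give, the disease share and the outcome gap between disease types, and the whole point depends on the *or* reading of eligibility.

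**What to change.** 1. Reconcile Protocol Sections 2 and 4 (either condition) with Section 9 (both conditions) and Section 21 (all with hypertension), and state which rule was applied at randomization. If every patient had both conditions, the rest is not needed.
2. If the sample is mixed, replace the change-score t tests and the significance-triggered score in Protocol Section 10 and the SAP with one arm-contrast ANCOVA for each of SBP, DBP, HbA1c and adherence: 3-month value on arm, baseline value and qualifying condition, the last two always included. If the planned tests have already been run, present this as an added analysis and label it so.
3. Report qualifying condition by arm, for those randomized and for completers.
4. Optional: stratify allocation by qualifying condition, preferably in two strata. This applies only if allocation is not complete, or to the larger trial.

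**Cost.** One to three model degrees of freedom at N = 40, using BP and A1c already measured before assignment. Stratifying would add one list and slightly unequal arm totals (at most 2 per stratum).

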### Data Analysis

**Creation of Individualized Adherence Profiles:** To create individualized adherence profiles, we will first use standard linear regression, modeling scheduling adherence metric values (transformed, if needed) for patients in terms of their scores on each available barrier variable from the tailoring survey. Barrier variables significantly related to patient adherence will be used to create individualized profiles through cluster analysis. We will use adaptive clustering methods to determine an appropriate choice for the clustering method and the number of clusters. For cluster analyses, all barrier variables will be transformed to have values between 0-1 so they are comparable; they will also be ordered so that larger scores indicate worse levels for the associated barrier. Clusters will then consist of disjoint subgroups of patients with similar scores on the transformed significant barrier variables and will correspond to distinct adherence profiles. The most salient barriers for an adherence profile will be those with relatively higher scores compared to other barriers. Different tailored intervention strategies will be developed for the adherence profiles, addressing the most salient barriers for those profiles. Each patient of the proposed study will be assigned to the individualized adherence profile whose centroid (i.e., the vector of averages of barrier scores for the profile) is closest to the vector of barrier scores for that patient.

### Analyses for the Primary Aim:

**Analysis for the Secondary Aim:** Feasibility of the intervention will be assessed through an ongoing formative evaluation to identify barriers and facilitators to implementation in

## PROTOCOL TITLE: Tailored Approaches to Improve Medication Adherence

a primary care setting, which will be used to inform necessary protocol modifications and continuously refine the methods. This will be achieved through informal interviews with clinic staff and an observational report created by [name] that will inquire about space requirements to implement the study, any changes in workflow that can be attributed to the implementation of the study (e.g., increase in patient-provider communication about adherence, increase in BP/glucose monitoring of high risk patients), and modifications that were made to the initial study design that are needed to support and maintain it after the proposed study has ended. We will also assess reach of the intervention, which will be assessed as the proportion of the target population who volunteer to participate in the study. For this study, baseline rates will be calculated to determine the ratio of eligible participants invited to participate vs. those that enroll in the study. Data collected on participant's sociodemographic characteristics (e.g., age, gender, educational attainment, income), health literacy, and comorbid conditions will be used to determine if there are any differences between eligible participants that do not enroll vs. enrollees. Independent t-tests and the chi-square statistic will be used to determine if there are any significant differences between the groups. Reasons for not enrolling in the program will also be documented. In addition to these outcomes, exit interviews will be used to assess participants' acceptability and satisfaction with the program and to acquire feedback with respect to barriers and facilitators of participation in the program.

### **Analysis for the Tertiary Aims:**

**The effect of treatment on adherence status at 3-months.** Adherence will be measured as a continuous variable. A linear regression will be performed using the final assessment of adherence as a response and randomization group as a predictor. Other variables that may potentially have an effect on adherence such as age, gender, level of education and comorbidity will also be included if these variables are not balanced between groups by the randomization or if they are determined by univariate analysis to be significantly predictive of adherence.

**The effect of treatment on BP reduction at 3-months.** BP will be treated as continuous systolic BP (SBP) and diastolic BP (DBP) variables measured at baseline and 3-months. The effect of treatment on these variables over time will be assessed using differences in differences estimation whereby pre-intervention SBP and DBP values are subtracted from post-intervention values, and change amounts by study group are compared using t tests. The significance level will be set at  $\alpha=.05$ . Analysis of covariance will be used in place of a t test, if covariates are needed.

**The effect of treatment on HbA1c reduction at 3-months.** HbA1c will be treated as a continuous variable at baseline and 3 months. The effect of treatment on HbA1c over time will be assessed using differences in differences estimation whereby pre-intervention HbA1c values are subtracted from post-intervention values, and change amounts by study group are compared using t tests. The significance level will be set at  $\alpha=.05$ . Analysis of covariance will be used in place of a t test, if covariates are needed.

**Data Management:** [name] will oversee the data management for this study. All data will be double entered by RAs and compared using automated comparison programs. Inconsistent data entry will be resolved against the raw data, and comparisons will continue until all inconsistency is removed. Periodically, [name] will review all data for duplicate records, illogical collection dates and contingencies, and outlier values using program syntax created for each file. Reasons for dropout and loss to follow-up will be tabulated by condition. The results of analyses using imputed values will be compared with the results obtained with only complete cases. If the results indicate that attrition is significantly related to one or more baseline variable, predicted values from a logit model will be used as a covariate in all subsequent analyses, thereby correcting for differential attrition. All randomized participants will be included using intent-to-treat analytic strategies. While randomization is expected to produce well-balanced groups, analyses will determine baseline differences between the groups on demographic or prognostic variables. If significant differences are found, these variables will be included in a logit model to predict group assignment, and predicted values from the final logit model will be used as a covariate in all subsequent analyses.

**Data Storage and Confidentiality:** PHI obtained during pre-screening (with a waiver of authorization) will not be retained unless the subject provides informed consent. Any PHI collected after informed consent will be entered as part of the data set. To ensure confidentiality, baseline and 3 month data will be associated with an individual participant only by an assigned identification number, the code for which will be kept in a password protected file accessible only by the study team. Procedures have been centrally developed to ensure the confidentiality of information, such as encrypting all data, storing all hard copies of study related data in locked cabinets, password protecting all electronic files, ensuring that participant information is not identified with participant names, and that analyses are conducted and reported by group rather than by individual participants. All data will be maintained on a secure, physical and password-protected central computer server. Prior to inclusion in any data set (internal and external), data will be stripped of all identifying information. Access to the HIPAA-compliant database will be controlled by passwords, which are encrypted and required to meet standard security requirements.

**Procedures for audiotapes:** In this study, audio recordings of the semi-structured interviews will be completed to identify themes related to barriers and facilitators of medication adherence. These data will be used to tailor the adherence intervention program. All recordings will be conducted in a private dedicated room at the primary care clinic. Permission and signed informed consent will be sought from participants to complete the audiotape interviews. All participants will be informed that audiotaping is optional and refusal to sign the informed consent will not limit their participation in the study. In addition, participants have the right to review the tapes and can request for withdraw of the tapes at any time after giving consent without penalty. In the event that a participant requests withdrawing tapes, the tapes will be erased and destroyed. Withdrawing tapes from the study will not impact the care that patient receives or provider delivers at the Ambulatory Care Practice. To ensure confidentiality, all tapes will be assigned a unique study identifier and will be stored in locked file cabinets in a

safe and secure dedicated room that only study personnel will be able to access. No names will be transcribed from the tapes to ensure that there is no identifiable information during the coding process and included in the report.

